3.4. MTD Definition

The estimated MTD is the dose level associated with approximately 27.5% of DLT-evaluable patients experiencing a DLT. The target interval for the DLT rate is (22.5%-32.5%). Due to the discreteness of the dose levels and in the interest of the safety of patients, the estimated MTD is the highest tested dose level with DLT rate ≤ 0.325 in at least 6-12 evaluable patients for DLT. The study aims to determine a MTD for a dose regimen that does not include a priming dose administered IV, and an independent MTD for an IV dose regimen that includes a priming dose. In addition, the study aims to determine a MTD for PF-06671008 administered SC and may also determine an independent MTD for a SC dose regimen that includes a priming dose.

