	n=2	n=3	n=4	n=5	n=6	n=7	n=8	n=9	n=10	n=11	n=12
0	E	E	E	E	E	E	E	E	E	E	E
1	S	S	S	S	E	E	E	E	E	E	E
2	U	D	S	S	S	S	S	S	E	E	E
3		U	U	D	D	S	S	S	S	S	S
4			U	U	U	U	D	D	D	S	S
5				U	U	U	U	D	D	D	D
6					U	U	U	U	U	U	U
7						U	U	U	U	U	U

D: De-escalate the dose; E: Escalate the dose; S: Stay at the dose; U: Unacceptable toxicity

Note: If one patient has a DLT event observed in a dose cohort with 1 patient enrolled, additional patients (eg, 1 or 2) may be enrolled for dose escalation assessment.

Dose escalation will stop under any of the following conditions:

- The maximum sample size has been achieved;
- 6-12 patients have been enrolled at a dose that is predicted to be the MTD;
- All doses explored appear to be overly toxic and the MTD cannot be determined.

Intrapatient dose escalation, other than the potential inclusion of priming doses, will not be permitted in this study.

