3.6. Recommended Phase 2 Dose (RP2D) Definition

The RP2D is the dose chosen for further study based on Phase 1 study results. If the MTD proves to be clinically feasible for long-term administration in a reasonable number of patients, then this dose usually becomes the RP2D. Further experience with the MTD may

result in a RP2D dose lower than the MTD (eg, if in the expansion part >25% of patients require a dose reduction due to toxicity, then the sponsor may convene a safety committee to determine if a lower RP2D needs to be determined).

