9.2. Statistical Methods and Properties

This study has been designed to establish the Maximum Tolerated Dose (MTD) defined as the dose that yields approximately 27.5% probability of DLT and considers equivalent doses that yield probability of DLT in the interval (Equivalence Interval) 22.5% to 32.5%. The 27.5% target was chosen based on safety considerations and is considered appropriate based on simulations and expert input. The prior distribution of DLT is set as a beta (0.5,0.5) and the threshold probability for early termination and dose exclusion is set to 0.95 as suggested

in the original mTPI method.¹¹ Similarly, doses with an incidence of DLT>32.5% (eg, 4 out of 10) cannot be selected as MTD although is allowed by the mTPI method.

The modified toxicity probability interval (mTPI) design uses a Bayesian statistics framework and a beta/binomial hierarchical model to compute the posterior probability of three dosing intervals that reflect the relative difference between the toxicity rate of each dose level to the target rate ($pT = 0.275$) (See [Appendix 7](#)). If the toxicity rate of the currently used dose level is far smaller than pT , the mTPI will recommend escalating the dose level; if it is close to pT , the mTPI will recommend continuing at the current dose; if it is far greater than pT , the mTPI will recommend de-escalating the dose level. These rules are conceptually similar to those used by the 3+3 design, except the decisions of an mTPI design are based on posterior probabilities calculated under a coherent probability model. Being a model-based design, mTPI automatically and appropriately tailors dose-escalation and de-escalation decisions for different trials with different toxicity parameters. More importantly, all the dose-escalation decisions for a given trial can be pre-calculated under the mTPI design and presented in a two-way table. The decision rules to “dose escalate” (E), “no change in dose” (S), “dose de-escalate” (D) or “dose de-escalate, unacceptable toxicity” (U) are described in [Table 2](#).

Table 6. Dose Escalation Levels for IV Administration

Dose Level	Dose (ng/kg)
1 (Starting Dose)	1.5
2	7.5
3	20
4	50
5	100
6	200
7	300
8	400

* Intermediate doses may be evaluated based on clinical findings (eg, a dose between 20 and 50 ng/kg).

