Cohorts of patients could receive doses already tested but a dose that is associated with decision “Dose de-escalate, unacceptable toxicity” cannot be revisited and no more patients should be treated at this dose or higher doses for the remainder of the trial.

The maximum sample size for Part 1 would be N=92 but actual sample size will depend on the underlying dose toxicity profile and variability in actual data realization.

The study will continue accruing until one of the three stopping conditions below is triggered.

The algorithm will stop if any of the following criteria is met:

1. The maximum sample size has been achieved.

2. MTD has been identified with sufficient accuracy: 6 to 12 patients have been accumulated on a dose that is currently estimated to be the MTD; or
3. All doses explored appear to be overly toxic and the MTD cannot be determined.

Due to binomial data variability in small samples, DLTs may be observed in a first cohort(s) by chance even when the true Probability (DLT) is fairly low. This could result in the estimated posterior DLT rate to exceed the targeted 27.5% very early in the trial, triggering an early stop when very few patients (2-4) have been treated. To prevent stopping the trial prematurely in such cases, a step-down option with a lower dose of 1.0 ng/kg is added to the dose grid. This dose will be explored only if a high DLT rate occurs in the first cohort assigned to 1.5 ng/kg, ie, it will not be used as a starting dose and the algorithm will always assign the first cohort of patients to 1.5 ng/kg.

The following table shows the probability of escalating to the next dose level for a range of underlying true DLT rates. For example, for a cohort size of n=3 and for a DLT that occurs in 10% of patients, there is a greater than 90% probability of escalating. Conversely, for a DLT that occurs with a rate of 70%, the probability of escalating is 3%. It is assumed that dose escalation occurs with either 0/3 or 1/6 patients with DLTs.

Probability of Escalating Dose

True underlying DLT rate	10%	20%	30%	40%	50%	60%	70%	80%	90%
Probability of escalating dose	0.91	0.71	0.49	0.31	0.17	0.08	0.03	0.009	0.001

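### The MTD rule keeps only the upper limit of the target interval, so a dose well below target can be reported as the MTD; the plan has no 'MTD not reached' outcome

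*Protocol*

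**What the plan says.** Protocol 3.4, repeated in SAP 2.2.4, ties the MTD to a DLT rate of about 27.5% and gives 22.5% to 32.5% as the target interval. Citing the discreteness of the doses and patient safety, it then sets the working rule: "the estimated MTD is the highest tested dose level with DLT rate" ≤0.325 in at least 6-12 evaluable patients.

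Protocol 9.2 adds a bar on the upper side only: "doses with an incidence of DLT>32.5% (eg, 4 out of 10) cannot be selected as MTD".

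One of the three stopping conditions is success at a dose. Section 3.2.2 words it as "6-12 patients have been enrolled at a dose that is predicted to be the MTD", and 9.2 as "6 to 12 patients have been accumulated on a dose that is currently estimated to be the MTD". The only outcome without an MTD is "All doses explored appear to be overly toxic and the MTD cannot be determined". I found no outcome in the visible text for the opposite case, where no dose is toxic enough.

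Table 2 gives Escalate for 0 DLTs at every number of patients, and for 1 DLT from 6 patients upward. Section 3.6 says that if the MTD is feasible for long-term use, "then this dose usually becomes the RP2D".

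**The concern.** The working rule drops the lower end of the interval that gives the MTD its meaning. It cannot separate a dose that is the maximum tolerated from one that is merely the highest tested with enough patients. If escalation ends while DLTs are rare, the report would name an MTD that readers take to mean about 27.5% DLTs, when the data point to a much lower rate.

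The MTD is the main conclusion of Part 1. Section 3.4 seeks it for up to four regimens (IV and SC, each with or without a priming dose), and it normally feeds the RP2D.

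The situation can arise in three ways: a top level is reached, the sample-size limit is reached, or the highest tested dose collects six or more patients outside the algorithm. On the last route, Protocol 3.1 allows about 5 additional patients after the initial 2-4 at 100 ng/kg or higher, which makes up to 7 to 9. Section 3.2 says their safety data help establish the MTD or RP2D.

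**Working it through.** **1. The plan's own figure.** Appendix 7, Scenario 1, has true DLT rates of 0.01, 0.02, 0.05, 0.08 and 0.12 and is labelled as having its MTD at level 5. Table 12 scores mTPI 0.90 correct, with average size 21.9 and 1.6 DLTs. I simulated 10,000 trials with these settings:
- Beta(0.5,0.5) prior and intervals cut at 0.225 and 0.325;
- exclusion of a dose when P(rate >0.275) exceeds 0.95;
- cohorts of 3 and five levels;
- stop when the next assigned dose already has 9 patients, with Escalate at the top level treated as Stay.

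The appendix does not give its exact stopping and selection code, so this is an assumed version.

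| Stop at | Table 13, correct | Reproduced (level 5 chosen) |
|---|---|---|
| 6 | 0.893 | 0.887 |
| 9 | 0.900 | 0.896 (size 21.9, 1.54 DLTs) |
| 12 | 0.956 | 0.952 |

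The figure is the frequency of choosing level 5. Appendix 7 defines a correct MTD as a dose whose true rate is 22.5% to 32.5%. The highest true rate in Scenario 1 is 12%, so no choice can qualify and the correct proportion is 0, for mTPI and for 3+3 alike. The doses labelled as MTD in Scenarios 2 to 5 have true rates of 0.25, 0.275, 0.275 and 0.32, all inside the interval, so only Scenario 1 is affected. In the stop-at-9 runs, 64% of all trials named level 5 the MTD with its Table 2-type decision at Escalate, and 29% did so with no DLT at that dose.

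**2. Which results can be an MTD.** Cells with 6 to 12 patients and observed rate ≤0.325:

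| n | DLT counts meeting the cap | Reading Escalate in Table 2 | Inside 22.5%-32.5% |
|---|---|---|---|
| 6 | 0, 1 | 0, 1 | none |
| 7 | 0, 1, 2 | 0, 1 | 2/7 = 0.286 |
| 8 | 0, 1, 2 | 0, 1 | 2/8 = 0.250 |
| 9 | 0, 1, 2 | 0, 1 | none (2/9 = 0.222) |
| 10 | 0-3 | 0, 1, 2 | 3/10 = 0.300 |
| 11 | 0-3 | 0, 1, 2 | 3/11 = 0.273 |
| 12 | 0-3 | 0, 1, 2 | 3/12 = 0.250 |

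Eligible: 2+3+3+3+4+4+4 = 23. Escalate: 2+2+2+2+3+3+3 = 17, or 16 if Appendix 7's instruction to remain at 2/10 is used. Inside the interval: 5. At n=6, 2/6 = 0.333 is barred, so both eligible results read Escalate.

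**3. What 0/6 says about the rate.** The prior Beta(0.5,0.5) with 0/6 gives Beta(0.5,6.5):
- P(rate <0.225) = 0.93;
- P(0.225 to 0.325) = 0.05.

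For 0/9, P(rate <0.225) = 0.97. For 1/6 the posterior is Beta(1.5,5.5) and P(rate <0.225) = 0.60, so the two eligible results at n=6 are not equally informative.

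**4. How often a barely toxic drug gets an MTD.** Simulated with protocol Table 2, cohorts of 3, stop at 6, 9 or 12 patients, and MTD taken as the highest dose with at least 6 patients and observed rate ≤0.325:

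| True DLT rate, same at every dose | Grid closed at 8 IV levels | Open grid, N=92 |
|---|---|---|
| 0% | 100% | 0% |
| 2% | about 97-100% | about 77-83% |
| 5% | about 90-99% | about 86-98% |

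Section 3.2.2 allows increases beyond the listed levels, so the open column is closer to the text for IV dosing. It ignores additional patients enrolled outside the algorithm. In every case where an MTD is named, its true rate is below 22.5%.

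**The case against.** **The declaration is not automatic.** A reader might infer that any drug without DLTs will be given an MTD. The documents do not support that. With 0 DLTs Table 2 keeps escalating, the IV ladder is not capped at 400 ng/kg, and on an open grid no dose reaches six patients. The 100% figure needs a closed top level. This stands, and it confines the point to regimens where escalation ends for another reason.

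**The stopping rule may not conflict with Table 2.** A reader might infer a flat contradiction between stopping for success and Escalate. Section 3.2.2 speaks of a dose predicted to be the MTD and links that prediction to mTPI; on that reading an Escalate cell is not a predicted MTD. Section 9.2 speaks of the current estimate, which points towards the 3.4 rule. The wording is ambiguous; a contradiction is not established.

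**An Escalate cell can be a proper MTD.** This is so when the next dose was tested and proved too toxic. The gap concerns only regimens where that did not happen.

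**Any safety cap passes safer doses more often.** A single dose meets the cap at n=6 with probability 0.97 at a 5% true rate and 0.48 at 27.5%. It is tempting to say that the rule favours non-toxic doses two to one. That ignores the choice of the highest eligible dose, so I do not rely on it.

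**The convention is visible.** Appendix 7 says that all doses in Scenarios 1 and 2 are below target, DLTs are reported by dose level, and the RP2D is a judgement. A reader of the tables would see 0/6. This softens the consequence, but does not justify the label or the score of 90% correct.

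**Conclusion.** The point holds as a fault in the definition and reporting of the primary Part 1 conclusion. The working rule in Protocol 3.4 and SAP 2.2.4 omits the lower end of the stated target, and no outcome exists for a regimen that never reaches it. Of the eligible cells, 17 of 23 read Escalate and 5 of 23 lie in the interval; 0/6 qualifies with posterior probability 0.93 of being below it. The clearest evidence needs no simulation: Scenario 1's 0.90 becomes 0 under Appendix 7's own definition.

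The conclusion is conditional on escalation ending before a higher dose proves too toxic. How often that happens depends on whether the grid has a top level, how many additional patients are enrolled, and how the stopping condition is read. It should be corrected, but it does not show that the trial will mislabel its dose.

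**What to change.** 1. In Protocol 3.4 and SAP 2.2.4, add a reporting outcome, 'MTD not reached; highest dose evaluated', with the DLT count and posterior interval. It would apply to a regimen in which no higher dose was found too toxic and the data at the selected dose indicate a rate below the target interval. State in advance the posterior probability that counts as such an indication, since 0/6 (0.93) and 1/6 (0.60) differ. A bare requirement of an observed rate of at least 22.5% would not work, because no count at n=6 or n=9 lies in the interval.
2. In Appendix 7, restate the Scenario 1 result or change the definition of correct, and revise the comparison with 3+3 to match.
3. The sponsor should reconcile the MTD definition (3.4 and SAP 2.2.4, including the unclear minimum of 'at least 6-12'), the success stopping condition (3.2.2, 9.2 and SAP 2.2.3) and the Escalate cells of Table 2. Which rule governs escalation, stopping or dose selection is for the sponsor to decide.

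Cost: items 1 and 2 are wording and need no extra patients. Item 3 could affect enrolment, depending on how the sponsor resolves it. Some regimens will be reported as 'MTD not reached', possibly many if the drug is well tolerated: in the Scenario 1 simulation, withholding the label from Escalate cells would cut level-5 declarations from 0.896 to 0.896 − 0.643 = 0.253.

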3.5. Dose Expansion Phase (Part 2)

The maximum sample size for each tumor indication (ie, TNBC, CRC and NSCLC) will be in the range n=10 to n=20. Enrollment of patients in one indication may be discontinued if minimal or no anti-tumor activity (eg, 0 or 1 response) is observed in the first 10 evaluable patients for that indication (see section [Sample Size Determination](#)).

3.6. Recommended Phase 2 Dose (RP2D) Definition

The RP2D is the dose chosen for further study based on Phase 1 study results. If the MTD proves to be clinically feasible for long-term administration in a reasonable number of patients, then this dose usually becomes the RP2D. Further experience with the MTD may

result in a RP2D dose lower than the MTD (eg, if in the expansion part >25% of patients require a dose reduction due to toxicity, then the sponsor may convene a safety committee to determine if a lower RP2D needs to be determined).

4. PATIENT SELECTION

This study can fulfill its objectives only if appropriate patients are enrolled. The following eligibility criteria are designed to select patients for whom participation in the study is considered appropriate. All relevant medical and non-medical conditions should be taken into consideration when deciding whether a particular patient is suitable for this protocol.

4.1. Inclusion Criteria

Patient eligibility should be reviewed and documented by an appropriate member of the investigator's study team before patients are included in the study.

Patients must meet all of the following inclusion criteria to be eligible for enrollment into the study:

1. For dose escalation (Part 1): Histological or cytological diagnosis of a tumor type with the potential to have P-cadherin expression (see [Appendix 2](#)). Patients with tumor types other than those listed in [Appendix 2](#) may be allowed to enroll based on emerging data and with the agreement of the sponsor. Patients must be refractory to, intolerant of established therapy known to provide clinical benefit for their condition, ie, patients must not be candidates for regimens known to provide clinical benefit.
2. For dose escalation (Part 1): Must have tumor tissue available for submission to the sponsor. Patients enrolled in Part 1 should have access to their archival formalin-fixed paraffin embedded material containing tumor that is of diagnostic quality and representative of their diagnosed malignancy or consent to undergo a biopsy during screening.
3. For dose expansion (Part 2): Histological or cytological diagnosis of previously treated CRC, TNBC or NSCLC with at least one measurable lesion, not previously irradiated, as defined by RECIST version 1.1 ([Appendix 4](#)). Patients must be refractory to, intolerant of established therapy known to provide clinical benefit for their condition, ie, patients must not be candidates for regimens known to provide clinical benefit.
4. For dose expansion (Part 2): Must have tumor tissue available for P-cadherin expression evaluation and must meet minimum required P-cadherin expression level (to be determined prior to activation of Part 2). Patients enrolled in Part 2 should have access to their archival formalin-fixed paraffin embedded material containing tumor that is of diagnostic quality and representative of their diagnosed malignancy.
5. For dose expansion (Part 2): Must have at least one tumor lesion, not previously irradiated, that is amenable to biopsy and must agree to undergo biopsies required per the [Schedule of Activities](#).

6. Age \geq 18 years.
7. Eastern Cooperative Oncology Group (ECOG) Performance Status (PS) must be 0 or 1.
8. Total body weight \geq 70 kg (154 lbs) for IV starting dose level only.
9. Adequate bone marrow function, including:
 - a. Absolute Neutrophil Count (ANC) \geq 1,500/mm³ or \geq 1.5 x 10⁹/L;
 - b. Platelets \geq 100,000/mm³ or \geq 100 x 10⁹/L;
 - c. Hemoglobin \geq 10 g/dL.
10. Adequate renal function, including:
 - a. Estimated creatinine clearance \geq 60 mL/min as calculated using the method standard for the institution.
11. Adequate liver function, including:
 - a. Total serum bilirubin \leq 1.5 x ULN unless the patient has documented Gilbert syndrome;
 - b. Aspartate and Alanine transaminase (AST and ALT) \leq 2.5 x ULN; \leq 5.0 x ULN if there is liver involvement secondary to tumor;
 - c. Alkaline phosphatase \leq 2.5 x ULN; (\leq 5 x ULN in case of bone metastasis).
12. Resolved acute effects of any prior therapy to baseline severity or CTCAE Grade \leq 1 except for adverse events (AEs) not constituting a safety risk by investigator judgment.
13. Serum or urine pregnancy test (for females of childbearing potential) negative at screening.
14. Male patients able to father children and female patients of childbearing potential and at risk for pregnancy must agree to use two highly effective method(s) of contraception throughout the study and for at least 28 days after the last dose of study treatment.

Female patients who are not of childbearing potential (ie, meet at least one of the following criteria):

 - Have undergone a documented hysterectomy and/or bilateral oophorectomy;
 - Have medically confirmed ovarian failure; or

- Achieved postmenopausal status, defined as follows: cessation of regular menses for at least 12 consecutive months with no alternative pathological or physiological cause; status may be confirmed by having a serum follicle-stimulating hormone (FSH) level within the laboratory's reference range for postmenopausal women.

15. Evidence of a personally signed and dated informed consent document indicating that the patient has been informed of all pertinent aspects of the study.
16. Patients who are willing and able to comply with scheduled visits, treatment plans, laboratory, tests and other procedures.

4.2. Exclusion Criteria

Patients with any of the following characteristics/conditions will not be included in the study:

1. Patients with known CNS disease including, but not limited to, metastases.
2. Current or history of seizure disorder.
3. History of or active autoimmune disorders (including but not limited to: Crohn's Disease, rheumatoid arthritis, scleroderma, systemic lupus erythematosus, Grave's disease) and other conditions that compromise or impair the immune system.
4. Active bacterial, fungal or viral infection including hepatitis B (HBV), hepatitis C (HCV), known human immunodeficiency virus (HIV) or acquired immunodeficiency syndrome (AIDS)-related illness.
5. Bleeding esophageal or gastric varices within 2 months prior to registration.
6. History of or current requirement for chronic blood product support.
7. Grade ≥ 2 peripheral neuropathy.
8. Pregnant female patients; breastfeeding female patients.
9. Major surgery within 4 weeks prior to registration.
10. Radiation therapy within 4 weeks prior to registration. Palliative radiotherapy to a limited field is allowed after consultation with the sponsor's medical monitor unless it is clearly indicative of disease progression.
11. Systemic anti-cancer therapy within 4 weeks of registration (6 weeks for mitomycin C or nitrosoureas). If systemic anti-cancer therapy was given within 4 weeks, patient may be included if 5 times elimination half-life of drug has passed.
12. Previous high-dose chemotherapy requiring stem cell rescue.
13. Requirement for systemic immune suppressive medication [eg, ≥ 10 mg of prednisone or equivalent (≥ 1.5 mg of dexamethasone)].

14. History of CTCAE Grade ≥ 3 immune-mediated adverse event (including AST/ALT elevations that were considered drug related and cytokine release syndrome) that was considered related to prior immune-modulatory therapy (eg, checkpoint inhibitors, co-stimulatory agents, etc.) or any-grade immune-related AEs that required immunosuppressive therapy.
15. Prior treatment with a compound of the same mechanism.
16. Any of the following in the previous 6 months: myocardial infarction, severe/unstable angina, coronary/peripheral artery bypass graft, symptomatic congestive heart failure, cerebrovascular accident, transient ischemic attack or symptomatic pulmonary embolism.
17. Participation in other studies involving investigational drug(s) within 28 days prior to registration.
18. Other severe acute or chronic medical or psychiatric condition, including recent (within the past year) or active suicidal ideation or behavior, or laboratory abnormality that may increase the risk associated with study participation or investigational product administration or may interfere with the interpretation of study results and, in the judgment of the investigator, would make the patient inappropriate for entry into this study.
19. Patients who are investigational site staff members directly involved in the conduct of the study and their family members, site staff members otherwise supervised by the investigator, or patients who are Pfizer employees directly involved in the conduct of the study.

